1.0 TRIAL SUMMARY

1.1 Objectives

1.1.1 Primary objective:

1.) To assess physician-reported acute grade 3 or greater gastrointestinal, genitourinary and hematologic toxicities at 12 weeks post-treatment for patients treated with linear energy transfer (LET)-optimized, intensity-modulated proton therapy (IMPT) and compare to contemporary controls treated with VMAT to determine the feasibility of this outcome for a future randomized trial.

1.1.2 Secondary objectives:

1.) To assess the feasibility of enrolling patients on a prospective trial delivering LET-optimized IMPT for newly diagnosed, non-metastatic anal cancer.
2.) To develop guidelines and workflow to create and deliver anal canal cancer treatments using LET-optimized IMPT.
3.) To evaluate complete response rate at 12 weeks and 24 weeks post-treatment.
4.) To evaluate local progression free survival, distant metastasis-free survival and overall survival at 24 and 48 months.
5.) To evaluate rates of patient-reported acute toxicity, function, distress and QOL at 12 weeks.
6.) To evaluate rates of patient-reported late toxicity, function, distress and QOL every 6 months for 24 months.
7.) To evaluate the value of proton therapy by comparing Time-Driven Activity-Based Costing data from the date of consultation until the date of the 12-week follow up visit post-treatment with contemporary controls treated with VMAT.

1.1.3 Exploratory objectives:

1.) To compare dose to the pelvic bone marrow, bowel, bladder and genitalia between LET-optimized IMPT, traditionally-optimized IMPT and VMAT.
2.) To assess rates of leukopenia, neutropenia and lymphopenia at 12-weeks post-treatment for patients treated with LET-optimized IMPT and compare to contemporary controls treated with VMAT.
3.) To correlate white blood cell counts (WBC), absolute neutrophil counts (ANC) and absolute lymphocyte counts (ALC) with dose to the pelvic bone marrow for patients treated with LET-optimized IMPT.

Abbreviated Title	IMPT for Anal Cancer
Trial Phase	Feasibility
Clinical Indication	Newly diagnosed, non-metastatic squamous cell carcinoma of the anal canal dispositioned to definitive chemoradiation treatment
Trial Type	Treatment
Type of control	None
Route of administration	External beam proton radiation therapy with concurrent chemotherapy
Trial Blinding	NA
Treatment Groups	Single arm, non-randomized
Number of trial subjects	40
Estimated duration of trial	9 years
Duration of Participation	9 years

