6.3 Post-treatment Follow-up Procedures

- 6.3.1 The treating physician or qualified designee will perform a focused physical examination at the first follow-up evaluation including documentation of clinical response to treatment (complete clinical response, partial clinical response/residual disease, or progressive disease). .
- 6.3.2 The treating physician or qualified designee will record weight at the first follow-up evaluation.
- 6.3.3 The investigator or qualified designee will assess performance status using the Eastern Cooperative Oncology Group (ECOG) Performance Scale at the first follow-up evaluation.
- 6.3.4 Endoscopic examination of the anal canal on either anoscopy, sigmoidoscopy or rigid proctoscopy at the time of the first follow-up evaluation (12+/-4 weeks from completion of CRT).
- 6.3.5 Contrast-enhanced CT scan of the chest, abdomen and pelvis with contrast at the time of the first follow-up evaluation (12+/-4 weeks from completion of CRT) unless the patient has a documented contrast allergy or inadequate renal function. The CT will be read by a staff radiologist as per the current standard of care. Dimensions of any residual tumor should be recorded where applicable.
- 6.3.6 Labs will be obtained at the first follow-up evaluation including complete blood count (CBC: hemoglobin, hematocrit, WBC with differential blood cell counts (neutrophils, bands, lymphocytes, monocytes, eosinophils, basophils) and platelets.
- 6.3.7 At the first follow-up evaluation, patients will report symptoms and quality of life with the following instruments as outlined below. Questionnaires will be administered electronically and paper copies of the questionnaires will be available if necessary.
 - The PRO-CTCAE
 - The EQ-5D.
 - The EORTC QLQ-C30 will be utilized to report GI-specific quality of life
 - The Perceived Stress Scale
 - For female patients:
Female Sexual Function Index (FSFI)- 19 question survey validated in cancer survivors.
 - For male patients:
Individual Items of International Index of Erectile Function Questionnaire (IIEF).

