6.5 Correlative Analyses

6.5.1 Both traditionally-optimized IMPT and LET-optimized IMPT plans will be generated for each patient enrolled on study. The goal of LET-optimized IMPT is to maximize the LET within the target and minimize it in normal tissues while maintaining the coverage requirements for target volumes and dose volume constraints for OARs expressed in terms of (RBE=1.1) weighted doses. This requirement is imposed to assure safety and for consistency with the current practice. The difference in dose distribution between IMPT and LET-optimized IMPT plans is expected to be minimal to moderate. Even though constraints are fully met, due to possible redistribution of high LET values from normal tissues into target volumes in LET-optimized IMPT plans, for some cases mean dose to surrounding critical organs may be increased. Our goal is to evaluate the safety of such differences in dose distributions.

6.5.2 Blood will be drawn at baseline, weekly during chemoradiation and at the 12-week post-treatment follow up visit as per standard of care (Table 1). WBC, ANC and ALC values will be recorded from the standard of care CBC drawn and their nadirs will be correlated with radiation dose to the pelvic bone marrow.

7.0 STASTICAL PLAN:

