7.4 Statistical Analysis Plan

7.4.1 Primary Clinical Endpoint: *To assess physician-reported acute grade 3 or greater gastrointestinal, genitourinary and hematologic toxicities at 12 weeks post-treatment for patients treated with linear energy transfer (LET)-optimized, intensity-modulated proton therapy (IMPT) and compare to contemporary controls treated with VMAT to determine the feasibility of this outcome for a future randomized trial.*

- At baseline, weekly during treatment, and at the 12 week post-treatment follow up appointment, the treating physician will document physician-assessed acute hematologic, gastrointestinal, genitourinary, dermatologic and other toxicities according to the Common Toxicity Criteria for Adverse Events v-4 (CTCAE v4).
- For each cumulative physician-reported toxicity (hematologic, gastrointestinal, genitourinary, dermatologic and other) at 12-weeks post-treatment, we will tabulate results by type, grade, and attribution and compare with contemporary controls treated with standard of care VMAT-based chemoradiation with 5FU and cisplatin for non-metastatic anal squamous cell carcinoma manually and individually matched for (in order): T-stage, radiation dose, age and gender. We will compare toxicity rates using a McNemar's chi-squared test for paired proportions.
- A separate PA protocol will be submitted to retrospectively review the data from these contemporary controls.
- Subset analyses will be carried out to evaluate the effect of other variables that may also impact toxicity in addition to radiation modality (IMPT vs VMAT).

On RTOG 0529, patients treated with dose-painted IMRT-based concurrent CRT for anal cancer had reported worst overall G3 or greater toxicity rates of 83%. GU/GI G3 or greater toxicity rates were 21%, dermatologic G3 or greater toxicity rates were 23% and hematologic G3 or greater toxicity rates were 58% ⁴.

To ensure an LET-optimized IMPT-based CRT approach is not overly toxic, we will monitor physician-assessed toxicity using the Bayesian optimal phase 2 (BOP2) design ²⁸. Specifically, let n denote the interim sample size and N denote the maximum sample size. Let p_{tox} denote the probability of G4 or greater toxicity and define the null hypothesis $H_0: p_{tox} > 0.5$, representing that the treatment is too toxic. We will stop enrolling patients and inspect the safety data for possible trial termination if

$$Pr(p_{tox} \leq 0.5 | data) < \lambda \left(\frac{n}{N}\right)^\alpha,$$

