- Exploratory Endpoint #2: *To assess rates of leukopenia, neutropenia and lymphopenia at 12-weeks post-treatment for patients treated with LET-optimized IMPT and compare to contemporary controls treated with VMAT.*
 - We will compare the on-treatment blood count nadirs for patients treated with LET-optimized IMPT with matched historical controls treated with VMAT (as described above). Continuous variables will be compared using a Wilcoxon-Rank-Sum test and corresponding p-values will be reported.
- Exploratory Endpoint #3: *To correlate white blood cell counts (WBC), absolute neutrophil counts (ANC) and absolute lymphocyte counts (ALC) with dose to the pelvic bone marrow for patients treated with LET-optimized IMPT.*
 - For each patient treated with LET-optimized IMPT, mean bone marrow dose and bone marrow V10 will be correlated with WBC, ANC and ALC nadir using the Spearman rank correlation coefficient to evaluate for correlation.
- Exploratory Endpoint #4: *To encourage optional co-enrollment on study 2014-0543 so that tumor DNA, rectal microbiome and MRI imaging-based biomarkers can be assessed for patients receiving LET-optimized IMPT and compared with other patients enrolled on 2014-0543 receiving VMAT-based radiation.*
 - Data from tumor swabs, tumor brushings and rectal swabs will be evaluated on 2014-0543 to identify mutations in cancer related genes enriched during the course of chemoradiation. Changes in tumor gene mutations are also correlated with protein phosphorylation status. Additionally, shifts in the microbiome occurring during the course of chemoradiation in the rectal flora.
 - Data from patients coenrolled on 2014-0543 receiving LET-optimized IMPT will be compared with patients enrolled on 2014-0543 only who receive VMAT-based chemoradiation.
 - We will use descriptive statistics and graphical methods illustrate genomic mutations and rectal flora from baseline at each assessment during chemoradiation (week 1, 3 and 5).

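### Exploratory Endpoint #2 asks for 12-week cytopenia rates against matched VMAT controls, but its stated analysis is an unpaired test on continuous on-treatment nadirs

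*Combined protocol and SAP*

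**What the plan says.** The endpoint in section 7.4.3 reads: "To assess rates of leukopenia, neutropenia and lymphopenia at 12-weeks post-treatment for patients treated with LET-optimized IMPT and compare to contemporary controls treated with VMAT". Exploratory objective 2 in section 1.1.3 is worded the same way.

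The analysis under that endpoint has two sentences. The first begins "We will compare the on-treatment blood count nadirs for patients treated with LET-optimized IMPT" and names matched VMAT controls as the comparator. The second reads: "Continuous variables will be compared using a Wilcoxon-Rank-Sum test and corresponding p-values will be reported". No count threshold, CTCAE grade or test of proportions is given there.

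The 12-week counts are collected. Section 6.3.6 states: "Labs will be obtained at the first follow-up evaluation including complete blood count", and Table 1 and section 6.5.2 agree. For WBC, ANC and ALC, section 6.5.2 goes on to say that "their nadirs will be correlated with radiation dose to the pelvic bone marrow"; it describes no analysis of the 12-week values.

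Section 7.4.1, under the primary endpoint, says that for each cumulative physician-reported toxicity, hematologic included, "at 12-weeks post-treatment, we will tabulate results by type, grade, and attribution and compare with contemporary controls". These controls are individually matched on T-stage, radiation dose, age and gender, and toxicity rates are compared by McNemar's test.

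**The concern.** The endpoint names a proportion at 12 weeks after treatment. The analysis tests a continuous value from the treatment period. The type of outcome and the time window both differ. The depth of suppression during chemoradiation and the presence of cytopenia 12 weeks later are separate questions, and marrow sparing is a main part of the rationale for IMPT in section 3.2.1.

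If the endpoint's own text is followed, a nadir comparison would be reported under a heading about 12-week rates. A reader could then take a difference in acute nadirs for a difference in cytopenia at 12 weeks, or take similar nadirs as evidence that 12-week rates do not differ. The rank-sum test also treats as independent two groups that the plan assembles as individual pairs.

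**Working it through.** The plan states no sample size, alpha, power or effect size for this endpoint, so there is no figure to reproduce. The check sets the texts side by side.

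**1. Endpoint against analysis**

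| Attribute | Endpoint (1.1.3 and 7.4.3) | Analysis under it (7.4.3) |
|---|---|---|
| Quantity | Rate (proportion) | Continuous count |
| Time | 12 weeks post-treatment | On treatment only |
| Case definition | Three named cytopenias, not defined | No cutoff or grade |
| Comparator | VMAT controls | Individually matched VMAT controls |
| Test | None named for a rate | Wilcoxon rank-sum (unpaired) |

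**2. Two readings of the 12-week time point**

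- *Value at the 12-week draw.* The rate is the number of patients below the cutoff at that draw divided by the number with a draw. An on-treatment nadir does not contain this value.
- *Cumulative through 12 weeks*, as section 7.4.1 words it. The rate is the number whose lowest count, over the weekly draws and the 12-week draw, falls below the cutoff. An on-treatment nadir is closely related to this, but it omits the last draw, and without a cutoff it is not turned into a rate.

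Neither reading gives a rate from the stated analysis.

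**3. Whether section 7.4.1 fills the gap**

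It grades hematologic toxicity by CTCAE v4 at baseline, weekly and at the 12-week visit, tabulates by type and grade, and compares rates as paired proportions. Three limits remain. First, Endpoint #2 does not point to it for analysis; its back-reference follows the mention of the controls. Second, the tabulation is cumulative, so a cytopenia that has recovered by 12 weeks counts the same as one still present. Third, section 6.2.3 lists individual GI, GU and dermatologic items to be graded but has no such list of hematologic events, so separate rates for the three cytopenias are likely but not assured.

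**4. Pairing**

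Section 7.4.1 treats the same matched design as pairs and uses McNemar. The rank-sum test does not use the pairing. The documents give no within-pair correlation, so this effect cannot be sized.

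**5. Illustration with assumed values only**

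Assume 40 pairs, log-normal counts with log-SD 0.5, correlation 0.3 between nadir and 12-week count, no correlation within pairs, cutoff 1.0 K/µL, two-sided 0.05 and 2,000 runs. Apart from 40, the plan's evaluable number, none of these comes from the documents. With median m, the 12-week rate is Φ(ln(1.0/m)/0.5).

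- *Equal nadirs (medians 0.5), 12-week medians 1.5 and 0.9.* The rates are Φ(−0.81) = 21% and Φ(0.21) = 58%. Rank-sum on nadirs rejected in 5% of runs, exact McNemar on 12-week rates in 90%.
- *Different nadirs (medians 0.7 and 0.45), 12-week medians both 1.2.* The rates are both Φ(−0.36) = 36%. Rank-sum on nadirs rejected in 97% of runs, McNemar in 3%.

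The scenarios were built to separate the two quantities. They show that the two tests can disagree in either direction, not that they would do so in this trial.

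**The case against.** The strongest reply is that cytopenia rates are largely handled in section 7.4.1. A by-type, by-grade hematologic tabulation would naturally include leukopenia, neutropenia and lymphopenia, and it is compared with the matched controls by a test suited to paired proportions. On this view a cross-reference is missing, not an analysis. Much of this stands.

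For that reason, some stronger readings are not supported. A reader might infer that the trial never compares these rates with VMAT, or that none of the three rates will be produced. The documents do not show this, because section 7.4.1 may produce cumulative versions. A reader might also infer that the 12-week counts of up to 40 patients go unused. That does not follow either: the counts are available to the CTCAE grading at the same visit. Moreover, 40 is the number evaluable for toxicity, which under section 7.3 requires only one weekly adverse event assessment and not a 12-week blood count.

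A second reply is that the 12-week phrase means cumulative, as in the primary endpoint, and that nadirs suit the rationale: section 3.1 cites an association of marrow dose with WBC and ANC nadirs, and Exploratory Endpoint #3 also uses nadirs. This narrows the time mismatch and is a good reason to keep the nadir comparison. It does not supply a cutoff or a rate, and it does not bring in the 12-week draw.

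Third, the endpoint is exploratory and carries no decision rule. This limits the weight of the point but does not reconcile the two texts.

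**Conclusion.** The mismatch holds. The analysis stated for Exploratory Endpoint #2 does not estimate the quantity that the endpoint names, under either reading of the 12-week time point, and it sets aside the matching. The conclusion rests on the wording alone; the simulation is not needed for it and says nothing about likely size here.

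The consequence is limited to this endpoint. The primary comparison and the safety stopping rule are unaffected. Section 7.4.1 may give cumulative hematologic rates, so what is clearly missing is a defined rate for each cytopenia tied to this endpoint and, if the 12-week draw is what is meant, any comparison specific to that draw. The point is worth correcting because the correction is cheap.

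**What to change.** Preferred change, in section 7.4.3:

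- For each of the three cytopenias, state the CTCAE v4 grade cutoff and whether the window is the 12-week draw (the visit is scheduled at 12 ± 4 weeks, that is 8 to 16 weeks) or cumulative through that visit.
- Compare paired proportions with the matched controls by McNemar's test, as in section 7.4.1. With n complete pairs, of which b have the cytopenia only in the IMPT patient and c only in the control, report the difference (b − c)/n with a 95% confidence interval, and report n.
- Keep on-treatment nadirs as a separately labelled comparison, with a paired test such as Wilcoxon signed-rank in place of rank-sum.

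Alternative: reword the objective in section 1.1.3 and the endpoint in section 7.4.3 as a comparison of on-treatment nadirs, analysed with pairing.

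Cost: both options are mainly wording changes. The first also needs grading of counts that are already collected for trial patients. Its downside is that some controls may lack a 12-week blood count, which reduces the number of pairs. The control data come under a separate retrospective protocol, so their availability should be checked before the window is fixed.

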4.0 INCLUSION AND EXCLUSION CRITERIA

4.1 Inclusion criteria

- 1.) Histologically-proven, non-metastatic invasive primary squamous cell carcinoma of the anal canal (Stages I, II, and III).
- 2.) History/physical examination within 60 days prior to registration.
- 3.) Anal examination with biopsy on either colonoscopy, sigmoidoscopy, rigid proctoscopy or anoscopy.
- 4.) CT scan of the chest and abdomen with contrast or contrast-enhanced PET/CT scan within 60 days of registration unless the patient has a documented contrast allergy.

- 5.) CT scan of pelvis with contrast or contrast-enhanced PET/CT scan within 60 days of registration unless the patient has a documented contrast allergy.
- 6.) Zubrod Performance Status of 0-1 within 60 days prior to registration.
- 7.) Age \geq 18 years – 85 years.
- 8.) Laboratory data within 30 days prior to study registration showing:
 - Absolute neutrophil count (ANC) \geq 1.8 K/ μ L
 - Cannot be achieved through GCSF use
 - Platelets \geq 100 K/ μ L
 - Cannot be achieved through transfusion.
 - Hemoglobin \geq 8g/dL
 - Cannot be achieved through transfusion.
 - Serum creatinine \leq 1.5mg/dL
 - Bilirubin \leq 1.4mg/dL
 - Except in the case of patients with Gilberts disease.
 - White blood cells (WBC) \geq 3000/microliter
 - AST/ALT < 3x the upper limit of normal
- 9.) HIV test must be done within 90 days of study registration. If HIV positive, CD4 count must be obtained within 90 days of study registration. Note: HIV positive patients are eligible for this study if they have a CD4 count >400 cells/mm3.
- 10.) The patient must either have insurance authorization or otherwise secure funding to cover IMPT.
- 11.) The patient must be able to receive concurrent chemotherapy.

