5.1.2 IMPT Planning and Plan Evaluation

The following is the series of steps in the IMPT planning process for each patient:

1. An MFO-IMPT plan will be designed using a commercial (clinical) treatment planning system (TPS) based on the current practice of using criteria defined in terms of dose- and dose-volume constraints and RBE = 1.1. (The Fixed RBE-IMPT plan.)
2. For the LET-optimized IMPT plan, dose distribution will be optimized using dose- and dose-volume criteria extended to include terms that increase LET in the target and reduce it in normal tissues. Such planning will require the use of an in-house TPS based on Monte Carlo techniques. Post-processing of scanning spots to ensure deliverability will also be performed as is done in the clinical TPS.
3. Both 1) IMPT and 2) LET-optimized IMPT will be reported in terms of three distributions: a) fixed RBE weighted dose (RBE=1.1), b) dose-averaged LET, and c) variable RBE-weighted dose (employing the RBE model of McNamara et al 2015) computed using Monte Carlo simulations. These distributions, dose- and LET-volume histograms and indices derived therefrom will be compared and presented to physicians to support decision making.
4. For safety considerations and for consistency with traditional practice, all dose distributions expressed in terms of RBE of 1.1 will be used to make final treatment decisions. To accomplish this, LET-optimized IMPT plan will be imported back into the current clinical TPS, Plan 1) and 2) will be renormalized to require the same target coverage and compared.
5. The dose distribution that best meets the dose requirements in the RBE=1.1 domain (Step 4) and maximizes the target LET while minimizes LET to critical structures (Step 3), as judged by the attending physician, will be chosen for treatment. If LET-optimized IMPT plan is not deemed significantly superior, the conventional IMPT plan will be chosen.
6. The selected plan will be approved in the clinical TPS and processed for quality assurance and treatment delivery.

5.1.3 GTV and CTV should be delineated on each axial slice of the planning CT scan on which they appear.

- GTVp includes the gross primary tumor in the anal canal as documented by physical exam, endoscopic exam, CT, PET and MRI.
- GTVn includes all involved nodes as documented by imaging or biopsy.
- CTVp includes the GTVp with a 1 cm margin except into uninvolved bone.

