6.1 Pretreatment Procedures

- 6.1.1 Patients will be screened for eligibility from 30 days prior to the start of CRT to the day of the start of CRT (provided that consents are signed before radiation treatment starts) (see section 4.0). A medical history will be obtained by the investigator or qualified designee. Medical history will include all active conditions, and any condition diagnosed that are considered to be clinically significant by the Investigator. Details regarding the disease for which the subject has enrolled in this study will be recorded separately and not listed as medical history.
- 6.1.2 The treating physician or qualified designee will perform a full physical examination at the first pretreatment evaluation including documentation of the primary anal lesion size and distance from the anal verge up to 30 days prior to registration.
- 6.1.3 The treating physician or qualified designee will record weight at the first pretreatment evaluation, weekly clinic visits and during follow-up).
- 6.1.4 The investigator or qualified designee will assess performance status using the Eastern Cooperative Oncology Group (ECOG) Performance Scale at screening and at every subsequent study visit.
- 6.1.5 Informed consent: the investigator must obtain document informed consent from each potential subject prior to participating in a clinical trial (Appendix).
- 6.1.6 MD Anderson pathology review of the biopsy specimen (if not performed at this institution) for histologic confirmation of squamous cell carcinoma. Human Papilloma Virus (HPV) determination will be noted from the biopsy specimen if available.
- 6.1.7 Endoscopic examination of the anal canal on either sigmoidoscopy or rigid proctoscopy will be completed prior to initiation of CRT and 7 days after initiation of CRT (although endoscopic examination prior to the start of CRT is strongly encouraged).
- 6.1.8 Contrast-enhanced PET/CT scan or CT scan of the chest, abdomen and pelvis with contrast up to 60 days prior to initiation of CRT unless the patient has a documented contrast allergy.
- 6.1.9 Baseline labs will be obtained, including complete blood count (CBC: hemoglobin, hematocrit, WBC with differential blood cell counts (neutrophils, bands, lymphocytes, monocytes, eosinophils, basophils) and platelets. Women of child-bearing potential require a urine pregnancy test (beta-hCG) prior to simulation.

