7.2 Enrollment

Anticipated enrollment is 1 patient every other month. We should be able to enroll 48 evaluable patients over 8 years. We anticipate 8 patients may not be evaluable such that we will have a total of 40 evaluable patients on this trial. Following enrollment of the last patient, we anticipate 6 months of follow up to obtain adequate toxicity data for the primary endpoint. Thus, we anticipate that this trial will take approximately 6-8 years to complete.

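### Exploratory Endpoint #3 correlates marrow dose with raw blood-count nadirs and leaves the collected baseline count unused; a baseline-adjusted coefficient reported alongside is a free, low-severity improvement

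*Combined protocol and SAP*

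**What the plan says.** Section 7.4.3, Exploratory Endpoint #3, specifies the whole analysis in one sentence: "mean bone marrow dose and bone marrow V10 will be correlated with WBC, ANC and ALC nadir using the Spearman rank correlation coefficient". That makes six coefficients, two dose measures by three cell counts, with no covariate. Section 6.5.2 describes the same analysis: the three counts are taken from routine blood draws and "their nadirs will be correlated with radiation dose to the pelvic bone marrow". Neither place mentions the starting count, a change or ratio from it, a partial correlation or a regression model.

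The starting count is available. Section 6.5.2 says "Blood will be drawn at baseline, weekly during chemoradiation and at the 12-week post-treatment follow up visit". Section 6.1.9 says "Baseline labs will be obtained, including complete blood count", with a differential that supplies neutrophils and lymphocytes. Table 1 schedules the same test at screening.

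The only covariate wording in section 7.4 is a general provision for subset analyses under the primary toxicity endpoint (7.4.1). It does not name baseline counts and does not extend to this endpoint.

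**The concern.** A nadir is the lowest value a patient reaches from his or her own starting point, so it may reflect the starting count as well as marrow dose. Section 4.1 ("Laboratory data within 30 days prior to study registration showing") sets floors for neutrophils and total white cells, but no ceiling and no limit for lymphocytes. Starting counts can therefore still differ between patients. Two consequences are possible.

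- **Loss of precision.** Spread in baseline counts that carries through to the nadir is noise in a raw dose-nadir correlation and shrinks it.
- **Bias.** Marrow dose is not randomly assigned. The prescription follows tumor or nodal size (5.1.5), and the marrow constraint is a guideline (5.1.7). If marrow dose happens to be related to the starting count, the raw coefficient mixes the two effects.

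At stake is how well a small exploratory data set can show a dose-count relation. Section 7.2 expects that "we will have a total of 40 evaluable patients on this trial". The number may be smaller here, because the endpoint is restricted to patients treated with LET-optimized plans and section 5.1.2 says "If LET-optimized IMPT plan is not deemed significantly superior, the conventional IMPT plan will be chosen".

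**Working it through.** The plan gives no significance level, target correlation, power or sample size for this endpoint, so there is no stated figure to reproduce. The check asks what omitting baseline would cost.

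**Inputs.** From the documents: n = 40 at most (7.2); Spearman correlation with no covariate (7.4.3). Assumed, because the documents are silent: two-sided 5%; a baseline-nadir correlation r_bn from 0 to 0.7; a baseline-dose correlation r_bd of 0 or ±0.3.

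**Formula.** With r_p the dose-nadir correlation given baseline,

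r_raw = r_p × sqrt((1 - r_bn²)(1 - r_bd²)) + r_bn × r_bd.

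When r_bd = 0 this reduces to r_raw = r_p × sqrt(1 - r_bn²). The identity is exact for ordinary correlations and approximate for ranks.

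**Step 1: adjusted analysis with 80% power.** On the Fisher z scale, with Spearman standard error 1.03/sqrt(n - 3 - k) and k = 1 covariate, SE = 1.03/sqrt(36) = 0.1717. The detectable size is tanh((1.960 + 0.842) × 0.1717) = tanh(0.481) = 0.447.

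**Step 2: raw analysis of the same truth, r_bd = 0.** Here k = 0 and SE = 1.03/sqrt(37) = 0.1693. Power = Phi(atanh(r_raw)/0.1693 - 1.960).

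| r_bn (assumed) | sqrt(1 - r_bn²) | r_raw | Power, raw | Power, adjusted |
|---|---|---|---|---|
| 0 | 1.000 | 0.447 | 81% | 80% |
| 0.3 | 0.954 | 0.426 | 77% | 80% |
| 0.5 | 0.866 | 0.387 | 67% | 80% |
| 0.7 | 0.714 | 0.319 | 50% | 80% |

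The shrinkage is 5%, 13% and 29% in the last three rows. At r_bn = 0 adjustment costs about one point of power.

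**Step 3: check by simulation.** Ranked trivariate-normal data, 20,000 data sets per scenario, r_p = -0.4 (assumed), r_bd = 0. Power of raw against partial Spearman:

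| r_bn | n = 40 | n = 30 |
|---|---|---|
| 0 | 68.9% vs 67.9% | 54.7% vs 53.5% |
| 0.3 | 64.1% vs 66.9% | 50.0% vs 52.5% |
| 0.5 | 55.1% vs 66.3% | 43.0% vs 52.1% |
| 0.7 | 40.0% vs 64.8% | 30.5% vs 50.1% |

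The pattern agrees with Step 2.

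**Step 4: if baseline and dose are related (r_bd = ±0.3, assumed), n = 40.**

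- *No true dose effect.* The raw coefficient averages about ±0.08, ±0.14 and ±0.20 at r_bn = 0.3, 0.5 and 0.7. Its false-positive rate is about 8%, 14% and 23%. The partial coefficient stays near 5%.
- *True r_p = -0.4, r_bn = 0.5.* The formula gives -0.4 × sqrt(0.75 × 0.91) ± 0.15 = -0.33 ± 0.15, that is -0.48 or -0.18. The simulated mean raw values are -0.45 for r_bd = -0.3 and -0.17 for r_bd = +0.3, against -0.38 and -0.36 adjusted. The raw value is exaggerated in one case and more than halved in the other.

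**The case against.** The strongest case against the point concerns its weight. This is the third exploratory objective. The plan sets no error rate, power or decision rule for it, so no power claim is broken, and the 80% reference was chosen here by solving for the effect that gives it. The baseline-nadir correlation is not in the documents, and near zero there is nothing to gain. The raw nadir is also a legitimate target: section 3.1 describes the earlier marrow-dose findings in terms of nadirs, and an unadjusted coefficient answers a marginal question that stays comparable with them. All of this stands. It lowers the severity and argues for reporting both coefficients instead of replacing one. It does not remove the gap, since the covariate is already collected and adjusting for it costs almost nothing.

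A reader might infer three stronger things that the documents do not support.

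- *That omitting baseline always weakens the correlation.* This holds only if baseline predicts nadir and is unrelated to dose. Step 4 shows that the raw value can also be inflated.
- *That a central claim of the trial is at risk.* The primary hypothesis (2.2) is that sparing organs at risk reduces toxicity, and section 3.1 treats the importance of marrow dose as already established. No stopping rule, sample size or conclusion depends on this coefficient.
- *That Exploratory Endpoint #2 can be adjusted just as freely.* Its VMAT controls come from a separate retrospective protocol (7.4.1). Their baseline counts are not shown to be available, and a rank-sum comparison would need a different, named method.

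**Conclusion.** The point holds as a low-severity improvement to an exploratory analysis. It is certain that the plan correlates raw nadirs with marrow dose and makes no use of the baseline counts it collects. The size of the consequence is conditional. With 40 patients, a two-sided 5% test, a true adjusted correlation of about 0.45 and baseline unrelated to dose, the raw analysis has about 77%, 67% or 50% power instead of 80% at assumed baseline-nadir correlations of 0.3, 0.5 or 0.7, and loses nothing if that correlation is near zero. Bias would require baseline count and marrow dose to be associated. Non-random dose makes this possible, but the documents do not show it, and its direction cannot be known in advance. The primary endpoint and the safety monitoring are unaffected.

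**What to change.** In section 7.4.3, Exploratory Endpoint #3, prespecify for each of WBC, ANC and ALC a partial Spearman correlation of the nadir with mean marrow dose, and separately with marrow V10, given the patient's own baseline value of the same count. Report each with a 95% confidence interval, and report the raw Spearman coefficient beside it. State which draw is the baseline, for example the last count before the first fraction, and bring section 6.5.2 into line.

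The cost is a line or two of text and one degree of freedom per coefficient; no new data are needed. Leave Exploratory Endpoint #2 as it is unless baseline counts for the VMAT controls are confirmed to be available and an adjusted method is named.
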